10.4.2. Modeling of continuous variables

To allow for non-linear covariate effects, the continuous variables of age, ejection fraction and eGFR will be modeled as restricted cubic splines with knots at the approximate 10th, 50th, and 90th percentiles of each variable's empirical distribution.

The proportionality assumption of the Cox model will be assessed by examining log-log survival plots and by adding a time-dependent covariate to the Cox model representing the interaction between treatment and time. If this interaction is large and statistically significant, then there is evidence of non-proportionality. In that case, a cautious interpretation of the Cox model hazard ratio will be encouraged, and non-parametric event rate estimates will be emphasized.

10.4.3. Missing data

Prior to selecting model covariates, participant baseline characteristics captured in the e-CRF were individually discussed by study investigators from the standpoint of prognostic significance and data

quality. With the exception of diabetes, covariates appearing in the model are required to be assessed by study coordinators for the purpose of determining trial eligibility and are therefore expected to be 100% complete on all participants. For example, participants cannot be randomized by the IXRS until after entering the participant's age and creatinine in the IXRS system. Missing, out-of-range, or illogical values will be identified by the SDCC and will result in queries to ensure complete high-quality data.

For each covariate to be used in the primary analysis, the number of missing records projected by study leadership is 10 or fewer. To make full use of the available covariate data, missing baseline covariate data will be imputed using multiple imputation statistical techniques. These techniques will account for additional variation in the analyses due to the fact that some of the data are missing. The imputation will use chained equations and predictive mean matching. Further details on what multiple imputation techniques will be used to impute missing baseline covariate data are found in the SAP Appendix for Multiple Imputation of Primary Baseline Covariates. Any rules of how to handle missing data prior to imputation are found in the SAP Appendix for Definitions and Reporting Conventions.

10.4.4. Additional supportive analyses for the primary endpoint

To supplement the conventional significance testing and confidence interval approaches that will constitute the major analyses for the primary endpoint, we will provide additional perspective on the assessment of the treatment effect by re-estimating the primary covariate-adjusted Cox model in a Bayesian statistical framework [11, 12]. Using the Bayesian posterior distribution, we will calculate the posterior probability that the unknown covariate-adjusted hazard ratio exceeds thresholds of 1.0, 1.05, 1.10, 1.15, and 1.20 and reciprocals of those numbers. Because Bayesian inferences may be sensitive to the choice of prior distribution, sensitivity analyses will be performed and reported for a range of possible prior distributions. Additional details of the proposed Bayesian model and prior distributions are provided in the SAP Appendix for Bayesian Analysis of Primary Endpoint.

10.5. Consideration for the analysis of the core-lab ischemia population

In October 2014, operating procedures for ISCHEMIA were modified to remove the requirement for pre-randomization core-lab determination of ischemia severity for most sites. The intent of this change was to simplify the work flow, increase the number of eligible participants, and improve site morale. It was determined that the imaging coordinating center would continue to interpret baseline stress tests for 100% of randomized participants, but the core-lab review may occur after randomization and would not determine a participant's eligibility. Under the new process, approximately 80% to 90% of randomized participants were projected to meet trial criteria by core lab interpretation.

- Primary analysis will be based on the ITT population which includes 100% of randomized participants.
- Analysis of the core-lab determined ischemia population will be a major secondary analysis.

Analysis of each of these cohorts is of interest for different reasons.

- Analysis of the ITT population is of particular relevance because real-world treatment decisions are based on local rather than core-lab interpretations of a patient's degree of ischemia. Except for possible administrative randomization errors, all participants in the ITT population will have moderate or severe ischemia by local site interpretation.

- The core-lab determined ischemia population is of particular interest because the efficacy of an invasive strategy as compared with a conservative strategy has never been tested in a large cohort of SIHD participants with core-lab determined moderate or severe ischemia. Theoretically, if the hypothesized benefit of an invasive strategy is concentrated in participants with moderate or severe ischemia, then the ITT treatment effect may be attenuated by unintentional inclusion of participants with mild or no ischemia.

Endpoint comparisons for the primary analysis will be repeated in the population of participants where the core-lab agreed that criteria for moderate or severe ischemia were met. As discussed in Section 10.6.3, results of the core-lab determined ischemia population will be stated in strict context by prioritizing the results of the ITT cohort and by noting the increased potential for a type-I error.

10.6. Analyses of heterogeneity of treatment effect (HTE)

Analyses of HTE will focus on estimating hazard ratios for INV versus CON as a function of participant baseline characteristics, as listed below. The list of primary baseline characteristics to use for the HTE analyses was intentionally limited to only a few variables in order to reduce the potential for spurious findings and to focus attention on variables that were most likely to interact with treatment based on prior literature and clinical experience.

10.6.1. Covariates for HTE analyses

Pre-specified baseline covariates (primary interest)

- Core-lab determination of moderate or severe ischemia on stress test
- Diabetes
- New onset or worsening angina within 3 months
- Participants who have a high level of medical therapy optimization at baseline, defined as participants with all of the following characteristics at baseline:
 - Systolic blood pressure < 140 mmHg (a secondary analysis will be completed incorporating a systolic blood pressure goal of < 130 mmHg)
 - LDL <70 mg/dL and on any statin
 - Not smoking
 - Taking aspirin

Another pre-specified baseline covariate of primary interest is the severity and extent of CAD as determined by core lab review of pre-randomization CCTA for those who have had that procedure completed.

Other pre-specified baseline covariates of interest

- Ejection fraction
- Estimated GFR

Ejection fraction and estimated GFR were not included in the list of pre-specified baseline covariates of primary interest due to the fact that it was anticipated that these covariates would have insufficient variation to be able to detect an appreciable difference in the treatment hazard ratios across the range of the covariates.

The following other baseline covariates are expected to be analyzed for descriptive purposes and completeness: age, sex, imaging modality (nuclear, echo, CMR, non-imaging ETT), prior MI, prior PCI, prior CABG, prior catheterization (≤ 12 months, > 12 months, none), severity of angina as assessed by the SAQ and Canadian Cardiovascular Society (CCS) Class.

Another pre-specified baseline covariate of interest is the presence of anterior ischemia for those participants with adequate stress imaging from the baseline screening process. **As discussed in Section 10.5, analysis of participants with core-lab determination of moderate or severe ischemia is of particular scientific interest and will constitute a major pre-planned secondary analysis.**

10.6.2. Assessment of covariate-by-treatment interactions

For each baseline covariate listed above, the Cox model described in Section 10.4.1 will be augmented to include the covariate (if it is not already in the model) and the interaction between the covariate and treatment group. A treatment-by-covariate interaction test will be used to assess whether variation in the estimated treatment effect across levels of the covariate is consistent with chance. Continuous covariates will be modeled as restricted cubic splines with three knots, requiring two parameters per variable with one of the parameters being for the non-linear effect. For categorical covariates, category-specific hazard ratios will be estimated and reported with 95% confidence intervals. For continuous covariates, covariate-specific hazard ratios will be estimated across the range of the continuous covariate and plotted as a continuous function and/or tabulated for representative numerical values of the covariate along with pointwise 95% confidence intervals.

10.6.3. Multiplicity considerations for HTE analyses

Statistical reporting of HTE analyses will emphasize estimation over hypothesis testing and will make liberal use of confidence intervals and other measures of statistical uncertainty. To provide context for interpreting treatment group comparisons within subgroups, subgroup-specific estimates will be accompanied by formal interaction tests. Differences in statistical significance of treatment effect estimates across subgroups will not be interpreted as evidence of heterogeneity. Because interaction tests are expected to have low statistical power for detecting a difference, these tests will be reported mainly for the purpose of encouraging readers to take an appropriately cautious interpretation of observed differences across the subgroups.

As noted above, the subset analysis of participants with core-lab determination of sufficient ischemia is regarded as a major pre-planned secondary analysis. To ensure an appropriately cautious interpretation of results for this cohort, the following reporting guidelines have been agreed upon by study leadership:

- If the 95% confidence interval for the hazard ratio excludes 1.0 (or, equivalently, the p-value is less than 0.05), the results section of the primary manuscript (as well as methods and discussion) should report that this confidence interval or p-value was not adjusted for multiple comparisons. The result should not be described as being "statistically significant" and the methods section should not state a p-value that was considered to be "statistically significant".

If the primary analysis fails to detect a difference in outcomes between the two randomized groups, the main conclusion of the study's primary manuscript will reflect the lack of significance for the primary analysis. In this setting, if the 95% CI for the hazard ratio comparing the primary endpoint for INV versus

CON excludes 1.0 in the subset of participants with core-lab determined moderate or severe ischemia, this result may be referenced in the conclusion of the study's primary manuscript, but the wording will be strictly consistent with the hypothesis that the observed result may be attributable to sampling variation. An example of wording that was regarded as appropriate by study leadership was: "In a pre-planned secondary analysis of participants with core-lab determined moderate or severe ischemia, participants assigned to the invasive [or conservative] strategy had a lower rate of cardiovascular death or myocardial infarction."

10.7. Analysis of angina control and QOL

Plans for these endpoints are addressed in a separate SAP developed by the Economics and Quality of Life (EQOL) Coordinating Center.

10.8. Analysis of protocol-defined secondary clinical endpoints

For these secondary clinical endpoints, including the major secondary endpoint of CV death or MI, analysis will be similar to the primary endpoint, using time from randomization until the first occurrence of the specific secondary endpoint as the response variable. Analysis of each secondary endpoint will be based on a covariate-adjusted Cox model with adjustment for variables specified in Section 10.4 above. For each secondary endpoint, non-parametric cumulative incidence estimates will be calculated by treatment group and reported with 95% confidence intervals. P-values for each secondary clinical endpoint will be individually calculated and reported without adjustment for multiple comparisons (see Section 10.12).

Just as what will be done for the analysis of primary clinical endpoints, multiple endpoint events in the same participant, such as a recurrent non-fatal event, will not be considered in the primary results analysis, but will be analyzed in planned secondary analyses.

10.9. Clinical endpoint data presentation

As described above, cumulative incidence estimates of endpoint probabilities will be displayed graphically and tabulated at yearly intervals following randomization along with two-sided 95% pointwise confidence intervals. In addition to these cumulative incidence estimates, the number of clinical endpoints by treatment group will also be presented. For MI, the number of CEC-confirmed endpoints will be reported overall, by UMI type (1, 2, 3, 4a, 4b, 4c, 5), and by presence/absence of the designation of "complicated MI", as defined in the CEC Charter, and "large MI". For these descriptive summaries, only the first MI event per participant will be counted. Not all of these analyses of MI data will be included in the primary manuscript.

10.10. Supportive analyses to quantify the size of MI's

To shed light on the size of MI's occurring in each treatment group, the distribution of CEC-determined highest marker elevation ratios (highest value divided by ULN as well as by the 99th percentile) will be summarized for all CEC-confirmed MI events with non-missing CKMB or troponin values. Summaries will be stratified by treatment group, MI type, and whether or not there was a Q-wave infarction. Marker elevation will be summarized by marker type, assay type, and/or degree of assay sensitivity. The resulting summaries will be regarded as informal descriptive statistics and will not be considered a primary or secondary protocol analysis.

10.11. Supportive analyses to adjust for treatment non-adherence

Although the proposed primary analysis will be a standard ITT analysis, additional secondary analyses may be performed using inverse-probability-of-treatment weighting estimators to assess the causal effect of treatment assignment had all participants adhered to their assigned treatment strategy.[13-16] This type of inference will be of particular interest if the study fails to detect a difference between INV and CON, as the observed treatment effect may have been attenuated by frequent non-adherence to protocol. An assessment of the causal effect of treatment assignment will also be addressed through the analyses of the primary and secondary endpoints in the Protocol Version 2.0 population. Detailed plans for these supportive analyses may be developed after completion of the primary analysis if this topic is prioritized by the publications committee. Simple methods of adjusting for non-adherence to the randomized treatment strategy, such as censoring at the time of crossover, will not be used in this study as they are susceptible to bias [17, 18] and do not estimate a well-defined parameter of interest. [16]

10.12. Multiple comparisons

With the various primary and secondary endpoints, and multiple subgroup analyses, we recognize that there is a multiplicity of analyses to be performed, which leads to an increased probability that at least one of the comparisons could be statistically "significant" by chance. Although the overall level of significance for the assessment of the primary composite endpoint will not be adjusted to account for the analysis of other important endpoints and subgroups, we will be appropriately conservative in the interpretation of these secondary analyses, taking into account the magnitude of observed differences, the robustness of statistical significance, and looking for consistency across endpoints and subgroups. It is important to emphasize that several of the secondary endpoints involve components of the primary endpoint, and therefore a major purpose in comparing the randomized groups with respect to these endpoints is to aid in the interpretation of any differences between groups observed in the primary endpoint. The actual p-value for each comparison will be reported to aid in the overall interpretation.

11. INTERIM ANALYSES

The primary objective of interim analyses is to ensure the safety of the participants enrolled in the trial and to evaluate the accumulating endpoint data by treatment group to test for possible differences favoring either of the two randomized management strategies. In addition, interim monitoring will involve a review of participant recruitment, compliance with the study protocol, status of data collection, an assessment of whether control group event rates are consistent with the rates hypothesized in the sample size calculations, and other factors which reflect the overall progress and integrity of the study including potential geographic differences. Details of the study's major planned interim analyses are documented below.

11.1. Violations of inclusion/exclusion criteria

The number of participants with violations of the inclusion/exclusion criteria will be presented. Eligibility criteria not met will be identified directly from the RANDIE (randomization inclusion/exclusion criteria) panel of the e-CRF or will be identified indirectly based on site- and core-lab entered data from the enrollment and randomization visits.

11.2. Completion of follow-up visits

Visit pages will be monitored for late entry in the clinical trial data base by the SDCC data management process. Additional summaries of visit completion by treatment will include the ratio of completed visits to expected visits and the percentage of visits performed within the expected visit time window. These visit completion summaries will also be completed for the final analysis.

11.3. Adherence to assigned treatment strategy

11.3.1. Use of catheterization and revascularization in INV

The INV strategy mandates use of early catheterization within a target of 30 days after randomization and revascularization soon thereafter, if appropriate, based upon coronary anatomy and other clinical considerations. To assess adherence to these requirements, the distributions of time from randomization to catheterization and time from randomization to revascularization will be estimated using the cumulative incidence function method for competing risks data.[6] For this analysis, participant follow-up will be censored at the date of last study visit. Death prior to catheterization or revascularization will be regarded as a competing risk. The cumulative proportion of participants receiving catheterization and revascularization will be estimated at specific time intervals (e.g. 30 days post randomization) both overall and within subgroups (e.g. prior CABG). For participants not undergoing catheterization by the time of the six-week and 3 month visits, the site-reported reason for no catheterization will be tabulated based on CRF-defined categories (participant preference, physician preference, intercurrent illness, participant died, other, unknown). For participants with site-reported planned medical therapy following catheterization, the reason for planned medical therapy will be tabulated according to CRF-defined categories (no obstructive CAD, anatomy not suitable for any mode of revascularization, participant preference, other).

11.3.2. Non-use of discretionary catheterization and revascularization in CON

The CON strategy mandates non-use of catheterization or revascularization procedures except in the case of suspected acute events (acute coronary syndrome, resuscitated cardiac arrest, or acute ischemic heart failure) or unacceptable angina refractory to maximally tolerated medical therapy. Catheterization or revascularization performed for other reasons, such as physician or participant preference, is considered non-adherence. A pattern of frequent early discretionary catheterization or revascularization in CON participants, especially those without prior endpoint events, may attenuate the treatment effect and cloud the interpretation of the study's primary ITT analysis.

Two types of analyses will be performed for estimating the cumulative incidence of catheterization and revascularization in the CON group. The first type of analysis will ignore the occurrence and timing of clinical endpoint events. The second type of analysis will only consider catheterization and revascularization procedures performed before the participant's first primary clinical endpoint event. The latter analysis is of particular interest because procedures performed after the occurrence of a clinical endpoint event will not impact power or interpretation for analyses of that type of endpoint. Quantities to be estimated will include all or a subset of the following:

- Cumulative incidence of catheterization for any reason
 - All
 - Occurring before participant's first primary endpoint event
- Cumulative incidence of catheterization for a suspected acute event

- All
- Occurring before participant’s first primary endpoint event
- Cumulative incidence of catheterization for site-reported OMT failure/refractory angina
 - All
 - Occurring before participant’s first primary endpoint event
- Cumulative incidence of catheterization for any other reason (non-adherence)
 - All
 - Occurring before participant’s first primary endpoint event
- Cumulative incidence of revascularization for any reason
 - All
 - Occurring before participant’s first primary endpoint event
- Cumulative incidence of revascularization for a suspected acute event
 - All
 - Occurring before participant’s first primary endpoint event
- Cumulative incidence of revascularization for site-reported OMT failure/refractory angina
 - All
 - Occurring before participant’s first primary endpoint event
- Cumulative incidence of revascularization for any other reason (non-adherence)
 - All
 - Occurring before participant’s first primary endpoint event

Incidence rates for each quantity listed above will be estimated using the cumulative incidence function method for competing risks data.[6] Participant follow-up will be censored at the last contact date or terminated after the participant’s death date, whichever occurs first. For estimating rates of catheterization and revascularization prior to endpoint events, occurrence of an endpoint event will be regarded as a competing risk. Reasons for catheterization will be based on the site-reported indication for the catheterization procedure as captured on the SITECATH1 form of the e-CRF. If one of the site-reported indications for the catheterization procedure includes MI, resuscitated cardiac arrest, or worsening or new onset heart failure, then the catheterization will be classified as “catheterization for a suspected acute event”. Otherwise, if one of the site-reported indications is “Failure of OMT/Refractory angina” then the catheterization will be classified as “catheterization for OMT failure/refractory angina”. Otherwise, if neither of the above conditions is met, the catheterization will be considered to be non-adherent to the CON strategy. Primary endpoints include MI, hospitalization for heart failure, hospitalization for unstable angina, and resuscitated cardiac arrest and will be based on best available data (i.e. adjudicated endpoints, if available, otherwise unadjudicated data will be used) while event adjudication is in progress. Endpoints occurring on the same day as catheterization or revascularization will be considered to occur before the catheterization or revascularization unless the endpoint was a PCI-related or CABG-related MI.

The main goal of the analyses described above is to monitor the frequency of transitions from the state of "no post-randomization catheterization" to "at least 1 post-randomization catheterization" in CON participants. Transitions occurring before the participant's first primary endpoint event are of particular concern because these have the potential to dilute power for the primary endpoint. Transitions occurring after a confirmed primary endpoint event will not dilute power because the endpoint is already counted.

Transitions occurring because of a suspected acute event or OMT failure may dilute power (because they occurred prior to a confirmed endpoint event) but are not violations of the CON strategy (because the strategy includes catheterizations performed in the case of a suspected acute event or OMT failure). Although these may dilute power, they do not necessarily reflect negatively on the study's conduct (because they are part of the treatment being studied).

An additional set of analyses will focus on estimating the underlying hazard rates of elective catheterization and elective revascularization in the CON group. The main goal is to shed light on the extent to which statistical power may be attenuated by catheterization or revascularization performed on a non-emergency basis in the CON group. Analysis will focus on estimating the underlying “intensity rates” of elective catheterization and revascularization (as opposed to the cumulative incidence function accounting for competing risks) because power calculations using multi-state models and accounting for treatment crossover typically require specification of such intensity rate parameters. Because the analysis focuses specifically on “elective catheterization” and “elective revascularization,” and to avoid counting catheterizations and revascularizations that may be true endpoint events, follow-up for these analyses will be censored 7 days prior to the participant’s first best-available composite endpoint event (death, myocardial infarction, hospitalization for unstable angina, hospitalization for heart failure, resuscitated cardiac arrest). The intensity rates of elective catheterization and elective revascularization will be estimated parametrically under an exponential and/or Weibull model and non-parametrically using a Nelson-Aalen type estimator. Because interpretable summary measures derived from the Nelson-Aalen estimator require the strong and arguably implausible assumption that elective catheterization and revascularization are independent of censoring and death, they will be regarded as informal and exploratory, and will be presented in the context of their inherent limitations.

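### SAP Section 11.3.2 defines the suspected acute events allowed in the conservative arm with one list and classifies catheterizations with another; unstable angina without MI is the main conflict

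*SAP*

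**What the plan says.** All the text at issue is in SAP Section 11.3.2, on non-use of discretionary procedures in CON.

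- **Definition.** CON rules out catheterization and revascularization "except in the case of suspected acute events (acute coronary syndrome, resuscitated cardiac arrest, or acute ischemic heart failure"), or for angina refractory to maximally tolerated medical therapy. It continues: "Catheterization or revascularization performed for other reasons, such as physician or participant preference, is considered non-adherence".
- **Data source.** "Reasons for catheterization will be based on the site-reported indication for the catheterization procedure as captured on the SITECATH1 form of the e-CRF".
- **Derivation rule.** The first step assigns the suspected-acute-event class: "If one of the site-reported indications for the catheterization procedure includes MI, resuscitated cardiac arrest, or worsening or new onset heart failure". The second step looks for an indication of failed optimal medical therapy (OMT) or refractory angina. The default follows: "Otherwise, if neither of the above conditions is met, the catheterization will be considered to be non-adherent to the CON strategy".
- **Endpoint timing.** Each quantity is listed in two versions, one covering all procedures and one covering only those before the first primary endpoint event. For the second, "For estimating rates of catheterization and revascularization prior to endpoint events, occurrence of an endpoint event will be regarded as a competing risk". Also, "Endpoints occurring on the same day as catheterization or revascularization will be considered to occur before the catheterization or revascularization", with an exception for PCI- or CABG-related MI.
- **Revascularization.** The same reason categories are listed again, for example "Cumulative incidence of revascularization for a suspected acute event". The section states a reason rule for catheterization only.

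Later in the section, the SAP says that catheterizations for a suspected acute event or OMT failure may dilute power but do not violate the CON strategy.

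**The concern.** The non-adherence category is how the SAP separates discretionary CON procedures from those that belong to the strategy. Section 11.3.2 attaches weight to that separation: it warns that frequent early discretionary procedures could attenuate the treatment effect and make the primary analysis harder to interpret, and it says that procedures within the strategy need not reflect badly on trial conduct.

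If the derivation uses a different list from the definition, the same catheterization can be permitted in one paragraph and non-adherent in the next. The reported non-adherence rate would then not measure what the section says it measures.

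**Working it through.** No arithmetic applies: the plan gives no figure for this point and no frequencies by indication. The check sets the two lists side by side and then traces which outputs depend on the difference.

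**Step 1. Compare the lists.**

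| Item | Definition of permitted CON procedures | Rule classifying catheterizations | Result |
|---|---|---|---|
| Coronary event | Acute coronary syndrome | MI | Rule narrower |
| Arrest | Resuscitated cardiac arrest | Resuscitated cardiac arrest | Match |
| Heart failure | Acute and ischemic | New onset or worsening | Rule broader |

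One item of three matches. The other two differ in opposite directions.

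**Step 2. Can MI in the rule be read to include unstable angina?** Not from the text. The same paragraph names hospitalization for unstable angina separately from MI among the primary endpoints, and Section 10.3 does likewise.

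**Step 3. Follow individual records through the rule.**

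- *Unstable angina or non-MI acute coronary syndrome as the sole indication.* The definition permits it. The rule finds no acute indication and no OMT failure, so the record defaults to non-adherent.
- *The same indication together with OMT failure.* The rule assigns OMT failure. The record stays permitted, so non-adherence is unchanged; at most, the split between the two permitted categories moves.
- *New or worsening heart failure that is not acute ischemic, as the sole indication.* It falls outside the definition's exceptions. The rule makes it a suspected acute event.

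**Step 4. Identify the exposed outputs.** Section 11.3.2 lists four catheterization categories (any reason, acute event, OMT failure, other reason), each in two versions: 4 × 2 = 8 quantities, of which the SAP commits to all or a subset. The 2 any-reason quantities do not use the rule. The remaining 3 × 2 = 6 do.

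- In the version covering all procedures, a catheterization for unstable angina alone is exposed whatever happens with endpoints.
- In the version before a first primary endpoint, it drops out if an endpoint is counted on an earlier day or on the same day. It stays exposed where the suspected unstable angina never becomes a counted endpoint, or where the first endpoint is dated after the procedure.

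**Step 5. Check the reach beyond catheterization.** If the catheterization rule is also applied to revascularization reasons, the matching revascularization estimates inherit the conflict. The section does not say whether it is.

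**The case against.** The strongest reply is that whether any record is misclassified depends on sources not available here. The rule works on SITECATH1 indications, and neither that form nor the SAP Appendix for Definitions and Reporting Conventions is in the reviewed text. The MI, arrest and heart-failure terms may abbreviate longer form options. If the form does not separate unstable angina from MI, the main conflict has no effect on the data. This stands, and the directional statements must therefore be conditional. It does not remove the conflict in the text, since the rule as written contains no such mapping.

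The heart-failure difference is also weaker than the coronary one. Every participant is meant to have stable ischemic heart disease with at least moderate ischemia, so new or worsening heart failure leading to catheterization may be a reasonable form-level proxy for a suspected acute ischemic event. This stands too, so the difference is treated as secondary.

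Finally, the consequence is small. The section's main aim is to monitor transitions from no catheterization to at least one, especially before a first endpoint. The any-reason estimates serve that aim and are unaffected, and the competing-risk and same-day rules remove many obvious unstable-angina cases from the version of particular interest. The analysis of elective-procedure intensity rates censors 7 days before the first composite event and does not cite the reason rule. All of this is accepted and is why the point is minor.

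A reader might go further and infer that CON non-adherence will certainly be overstated, or that the two differences cancel out. The documents support neither reading, because they show neither the form options nor any counts by indication.

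**Conclusion.** The definition and the derivation rule in Section 11.3.2 conflict, and this is minor. The main conflict is that a CON catheterization for unstable angina or non-MI acute coronary syndrome alone is permitted by the definition but labelled non-adherent by the rule. Reported non-adherence would be too high by those cases if SITECATH1 records that indication separately from MI. The heart-failure wording could shift the figure downward if the form distinguishes acute or ischemic heart failure from other heart failure. The net direction and the number of participants cannot be determined from the documents.

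The effect reaches the reason-specific CON catheterization estimates, mainly in the version covering all procedures, and the revascularization estimates if the same rule governs them. A reader might infer that the main result is compromised. The documents do not support that: the primary comparison is by intention to treat on adjudicated endpoints, and neither it nor alpha nor the sample size uses this classification.

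**What to change.** First check the indication options on SITECATH1 and any mapping in the Definitions and Reporting Conventions appendix. Then reconcile the two paragraphs of Section 11.3.2 so that the definition of permitted CON procedures and the derivation rule use one list of indications. That list should state explicitly how acute coronary syndrome and unstable angina are handled and should use the same heart-failure wording in both places. State also whether the rule governs the revascularization reason categories, and update the derivation code to match.

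No position is taken on which list is right or on what the strategy should permit; that is for the sponsor to settle.

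The cost is a sentence or so of SAP text and a small code change. No new data collection is needed if the form already records the indications separately.
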